**Figure 9. 2-Vessel Disease Treatment: 2 Target Vessels.**

**Figure 10. 2-Vessel Disease Treatment: 1 Target Vessel / 1 Non-Target Vessel.**

[figure not shown]

Figure 11. 3-Vessel Disease Treatment: 1 Target Vessel / 2 Non-Target Vessels.

[figure not shown]

Figure 12. 3-Vessel Disease Treatment: 2 Target Vessels / 1 Non-Target Vessel.

#### 6.5.4 Post procedure

All patients must have either a troponin level and/or a CKMB level (CK-MB preferred) drawn at 6-10 hours post PCI. The same biomarkers as those drawn at baseline should be assessed post-PCI. If the results are abnormal (>upper limits of normal), regardless of clinical significance, or if any procedural complications developed (temporary or sustained TIMI flow <III (visually assessed) in any vessel, or dissection  $\geq$  NHLBI type B, or perforation, or prolonged ST-segment elevation or depression (>5 minutes), or cardiac arrest or need for defibrillation or cardioversion or hypotension /heart failure requiring mechanical or intravenous hemodynamic support or intubation), a second post-PCI troponin level and/or CK-MB level must be drawn at 6-10 hours after the first post-PCI biomarker draw or at discharge. In the event of high sensitivity troponin use (which is not recommended), an elevation of <7X ULN in the first (6-10 hr) post-PCI blood draw will not require an additional level, unless any procedural complications developed.

At least one 12-lead ECG must be performed within 24 hours post PCI in all patients.

A serum creatinine level must be drawn the calendar day after PCI or before discharge, whichever is earlier. If the subject develops contrast induced nephropathy (defined as an increase in serum creatinine  $\geq$ 25% or an absolute increase of  $\geq$ 0.5mg/dl (44.2 $\mu$ mol/L)), regardless of clinical significance, it is recommended that serial creatinine levels be drawn daily until the peak is reached and the creatinine is decreasing.

A serum hemoglobin must also be drawn the calendar day after PCI or before discharge, whichever is earlier. If the subject develops overt bleeding, or the hemoglobin level has fallen more than 3 g/dL (30 g/L) in the absence of overt bleeding, serial hemoglobin levels must be drawn at least daily until a nadir is reached or the hemoglobin level has stabilized.

The following considerations apply to subjects having staged procedures:

- The protocol required post-procedure serum creatinine, cardiac enzyme and 12-lead ECG assessments must be repeated for the staged procedure as done for the original index procedure.
- The follow-up regimen of aspirin and P2Y12 receptor inhibitor (dosage requirements and timing) must be maintained following the staged procedure as done for the original index procedure.
- The follow-up period is considered as having begun upon completion of the original index procedure.

The timing and method of vascular sheath removal, as well as timing of ambulation, use of post-procedural medications and discharge is per standard of care. Aspirin must be continued indefinitely. DAPT must be continued for at least 6 months in patients with stable CAD and for at least 12 months in patients who presented with acute coronary syndrome unless the patient is also taking chronic oral anticoagulation in which case a shorter duration of DAPT may be prescribed per local standard of care. Post-procedural medication use should not vary according to randomization assignment.

#### 6.5.5 Scheduled Follow-ups

All patients enrolled in the study will be followed with clinic visit or phone calls at 30 ( $\pm$ 7) days, 1 year ( $\pm$ 30 days) and 2 years ( $\pm$ 30 days) by the authorized study personnel at the study site.

- 30-day Follow-Up

Telephone or clinic visit follow-up at 30 days ( $\pm$  7 days) including:

- Adverse events, medications, laboratory tests and 12-lead ECGs (if performed)
- 12 Month Follow-Up  
Telephone or clinic visit follow-up at 12 months ( $\pm$  30 days) including:
  - Adverse events, medications, laboratory tests and 12-lead ECGs (if performed)
- 24 Month Follow-Up  
Telephone or clinic visit follow-up at 24 months ( $\pm$  30 days) including:
  - Adverse events, medications, laboratory tests and 12-lead ECGs (if performed)

## 6.6 Patient Reported Outcome (PRO) Measures

The Study Coordinator or designee will administer patient-reported outcome questionnaires. It is important the subject understands the meaning of all words and instructions in the questionnaires. The subject should be instructed to ask any questions about the questionnaires if further explanation is needed. Once the questionnaires are completed, the Study Coordinator or designee will review for completeness to verify that all questions have been answered according to the directions provided.

The following PRO measures will be collected according to the study requirements.

- EuroQoL 5D (EQ-5D-5L) to assess Overall Health Status in hospital (required at baseline, optional post-procedure), and at 30 day, 12 month and 24 month follow-up

## 6.7 Unscheduled Visits

Any patient, who develops cardiac symptoms or a major adverse cardiac event during the follow-up period should be evaluated by the investigator by telephone contact or clinic visit as deemed appropriate.

Requisite data are listed:

- Adverse events, medications, laboratory tests and 12-lead ECGs (if performed)

For any occurrence during follow-up of an ADE/SAE or potential TVF or MACE event, detailed records of that event, including but not limited to hospitalization records (admission record, discharge summary, catheterization and operative reports, and other supporting data as required) must be collected and sent to the Sponsor. Any follow-up angiograms and OCT imaging studies must be sent to the core laboratory for analysis.

For all randomized patients returning to the enrolling institution during the follow-up period with a cardiac event that requires cardiac catheterization, OCT imaging should be conducted at the time of the catheterization in the target vessel coronary distributions (both in the OCT-guided and angiography-guided patients). A three-vessel angiogram should also be performed. These studies must be submitted to the core laboratory for analysis. These additional steps should never unduly jeopardize patient safety. If a patient develops any TVF or MACE event, or requires repeat hospitalization or repeat angiography following the index catheterization, these events must be documented in the eCRF. Copies of charts, lab values, examinations and a copy of the angiogram and all diagnostic procedures performed (e.g. OCT) must be submitted to the Sponsor.

### 6.8 Schedule of Events

Assessment	Baseline/ Procedure	Procedure (Randomized to OCT)	Procedure (Randomized to Angiography)	Post- Procedure ( $<24$ hours) 	30 Day ( $\pm 7$ days) 	12 Month ( $\pm 30$ days) 	24 Month ( $\pm 30$ days)	Unscheduled Visit 
Demographics and Medical History	X							
Physical Exam	X							
Pregnancy Test 	X							
12 Lead ECG	X			X				
Syntax score 	X							
Serum Creatinine	X 			X 				
Hemoglobin	X 			X 				
Troponin or CK-MB	X 			X 				
Angiogram	X							
Pre-PCI OCT		X						
PCI		X	X					
Post-PCI OCT		X	X 					
Cardiac Medications	X			X	X	X	X	X
Adverse Event		X	X	X	X	X	X	X
EQ5D	X 			X 	X	X	X	

 For women of childbearing potential

 Not required for subjects with single-vessel or simple 2-vessel disease

 Serum Creatinine and hemoglobin within 1 week prior to PCI.

 Baseline Troponin level or CK-MB: this may be drawn from the vascular sheath prior to PCI in subjects with stable coronary artery disease; labs must be drawn within 48 hours prior to PCI

 Post-Procedure Troponin level or CK-MB to be drawn at: 1) 6-10 hours post PCI; 2) if the first post-PCI biomarker is abnormal ( $>$ upper limits of normal), or if any procedural complications developed (see **Section 6.5.4** for details), a second post-PCI troponin level and/or CK-MB level must be drawn at 6-10 hours after the first post-PCI biomarker draw or at discharge. In the event of high sensitivity troponin use (which is not recommended), an elevation of  $<7X$  ULN in the first (6-10 hr) post-PCI blood draw will not require an additional level, unless any procedural complications developed.

 Post-Procedure creatinine and hemoglobin to be drawn at the calendar day post PCI or at discharge, whichever is earlier

- If the first creatinine draw indicates contrast induced nephropathy (absolute increase  $>0.5$ mg/dl (44.2 $\mu$ mol/L) or  $>25\%$  or the pre-procedure value) it is recommended that creatinine be drawn daily until the peak is reached and the creatinine is decreasing. If the subject develops overt bleeding, or the hemoglobin level has fallen more than 3 g/dL (30 g/L) in the absence of overt bleeding, serial hemoglobin levels must be drawn at least daily until a nadir is reached or the hemoglobin level has stabilized.

 Office visit or Telephone when last subject enrolled reached 12-month follow-up, excluding subjects with follow-up completed within 30 days

 Blinded

 Required at baseline in subject in whom randomization is likely or definite, optional at post-procedure

 Roll-In subjects are followed through post-procedure visit

 For unscheduled visits, procedure details, tests and medications will not be recorded in the database

## **6.9 Health Care Economic Data Collection**

Data on cardiovascular-specific resource utilization and will be collected prospectively for the index hospitalization and the full follow-up period using standardized case report forms. Procedural costs will be assessed using a resource-based approach to convert standard measures such as procedural duration and device utilization (e.g., stents, balloons, guidewires, etc.) into costs. Other hospital costs will be assessed using an “event-driven” approach in which specific complications and outcomes are assigned standard costs based on external data. Additional costs will be assigned for follow-up hospitalizations and repeat revascularization procedures, emergency room visits, outpatient diagnostic testing, and cardiovascular medications. In each case, costs will be assessed from the perspective of the U.S. healthcare system.

Cost and quality of life data will be used to perform a cost-effectiveness analysis from the perspective of the U.S. healthcare system.

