## 12) Procedure time (first wire insertion to guide catheter removal), fluoroscopy time, radiation exposure

13) Contrast use; contrast induced nephropathy (defined as serum creatinine rise  $>25\%$  or absolute increase  $>0.5$  mg/dL ( $44.2\mu\text{mol/L}$ )); need for renal replacement therapy

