### **Cost-effectiveness**

Cost per quality adjusted life year (QALY) and TVF event prevented by OCT-guidance to be determined using standardized methods.

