#### **6.5.3.2 Randomization to angiography-guided stenting**

If the patient is randomized to angiography-guided stent implantation, stenting will be performed and optimized with angiography guidance according to local standard practice. Quantitative coronary angiography (QCA) is not required. At the end of the stent procedure, at the time the operator would be otherwise removing the guidewire and taking final completion angiography, a blinded OCT must be performed for submission to the core laboratory. This blinded OCT run is for study purposes only – the operator may not view the OCT results, and may not make additional treatment decisions on the basis of this OCT image acquisition. To do so will be considered a major protocol violation.

The operator may obtain feedback from a member of the team, such as a technician, nurse, study coordinator etc. as to whether the final blinded OCT run was technically adequate, with good lumen clearance, capturing at least 10 mm distal and 10 mm proximal to the stented segment. At least 100 µg of IC nitroglycerin or appropriate dosage of IC isosorbide dinitrate should be administered for each target vessel treated prior to the final angiographic and OCT images, unless precluded by low blood pressure. Following the blinded OCT run, a final test coronary contrast injection or recorded cine angiogram may be taken to insure vessel patency without complication. In the event the index procedure in the angiography guided arm becomes prolonged and a second procedure is needed to complete stent implantation, the blinded OCT run may be performed in the second procedure when the operator deems that target vessel treatment is complete. No other intravascular imaging may be performed, and no additional treatment decisions may be made on the basis of the OCT image acquisition.

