At least 100 µg of IC nitroglycerin or appropriate dosage of IC isosorbide dinitrate must be administered for each target vessel treated prior to the final angiographic and OCT image acquisition, unless precluded by low blood pressure.

OCT images should be acquired using a 75 mm pullback over 2.1 seconds accruing 5 frames per mm. For standard pullback using power injectors (recommended) such as the ACIST or Medrad device, the recommended contrast injection volume is 14 ml at an injection rate of 4 ml/s in the left coronary artery and 12 ml at an injection rate of 3 ml/s in the right coronary artery. For large vessels, excessive tortuosity or lesions in the distal 3rd of the culprit vessel, 4 ml/sec for 4 seconds and thus 16 mL of contrast is recommended. For operators using manual injection, the recommended contrast injection volume is 14 ml in

the left coronary artery and 12 ml in the right coronary artery. Performing cine angiography in the desired angiographic view(s) during OCT pullback to maximize utility of delivered contrast is mandatory.

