- v. Post-PCI target vessel TIMI flow rate
 - vi. Angiographic complications – worst (anytime during the procedure) and final (post PCI and all imaging) - Angiographic dissection \geq NHLBI type B, perforations (Ellis classification), intra-procedural thrombotic events (including slow-flow, no-reflow, side branch closure, distal embolization, and intra-procedural stent thrombosis, as per the standard angiographic core laboratory definitions
- 11) Device Usage Endpoints (site reported; assessed per subject):
- i. Total stent length
 - ii. Total number of stents
 - iii. Maximal stent size
 - iv. Post dilatation (yes/no)
 - v. Total number of post-dilation balloons
 - vi. Maximal post-dilatation balloon size
 - vii. Maximal device size (stent or post-dilatation balloon)
 - viii. Maximum inflation pressure (atm.; stent or post-dilatation balloon)
- 12) Procedure time (first angiogram to guide catheter removal), fluoroscopy time, radiation exposure
- 13) Contrast use; contrast induced nephropathy (defined as serum creatinine rise $>25\%$ or absolute increase >0.5 mg/dL ($44.2\mu\text{mol/L}$)); need for renal replacement therapy
- 14) Procedural success (must be present in all treated lesions and vessels):
- Defined as A) angiographic core laboratory-assessed final (post-PCI) lesion angiographic diameter stenosis $<30\%$ and target vessel TIMI III flow without any of the angiographic complications listed in 10(vi) above; plus B) the absence of site-assessed prolonged ST-segment elevation or depression (>30 minutes), cardiac arrest or need for defibrillation or cardioversion or hypotension/heart failure requiring mechanical or intravenous hemodynamic support or intubation, or procedural death.

Abbott

Study Name: ILUMIEN IV

Statistical Analysis Plan

15) Procedural complications

Defined as A) angiographic core laboratory-assessed complications listed in 10(vi) above occurring anytime during the procedure; or B) site-assessed prolonged ST-segment elevation or depression (>30 minutes), cardiac arrest or need for defibrillation or cardioversion or hypotension/heart failure requiring mechanical or intravenous hemodynamic support or intubation, or procedural death.

16) OCT performance success (site reported) (OCT arm only):

OCT imaging performed both pre- and post-PCI

17) OCT imaging-related procedural complications (CEC adjudicated)

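### The angiography arm's research-only OCT run is counted in its procedure time, contrast and duration-based cost, so the comparisons understate what OCT guidance adds

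*Protocol*

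**What the plan says.** Protocol 6.5.3.2 requires the run in the angiography arm: "at the time the operator would be otherwise removing the guidewire and taking final completion angiography, a blinded OCT must be performed". It gives the reason: "This blinded OCT run is for study purposes only". The operator may not see the images or act on them. SAP 6.5 classes a target vessel left without this run as a major protocol deviation, so it is expected in every target vessel.

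Protocol 5.3.3 lists as endpoint 12 "Procedure time (first wire insertion to guide catheter removal), fluoroscopy time, radiation exposure". The corresponding item in SAP 5.5 is "Procedure time (first angiogram to guide catheter removal), fluoroscopy time, radiation exposure". The starting points differ, but both clocks stop when the guide catheter comes out. Endpoint 13 begins "Contrast use; contrast induced nephropathy (defined as serum creatinine rise" and continues with the thresholds. It does not say which contrast is counted. SAP 5.5.1 summarises continuous procedural endpoints by randomized arm, with no visible adjustment.

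On cost, Protocol 6.9 says "Procedural costs will be assessed using a resource-based approach to convert standard measures such as procedural duration and device utilization", from the perspective of the U.S. healthcare system. The aim in Protocol 5.3.3 is "Cost per quality adjusted life year (QALY) and TVF event prevented by OCT-guidance to be determined using standardized methods".

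**The concern.** A run that exists only to supply the imaging endpoint is not part of angiography-guided care. If its time and contrast stay in the control arm, the comparison becomes OCT guidance against angiography plus one OCT run. The cost-effectiveness aim concerns OCT guidance against angiography guidance.

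The error has a known direction: it makes OCT guidance look quicker, lighter on contrast and cheaper. Where OCT guidance shows a benefit, a smaller incremental cost lowers both the cost per QALY and the cost per TVF event prevented. The protocol treats these quantities as important. Section 3 gives cost and laboratory workflow as reasons why OCT may not suit every lesion, and section 8.1 says that OCT needs extra contrast, which may raise the risk of kidney injury.

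**Working it through.** The documents give no figure for this effect, so there is nothing to reproduce. The check has two parts.

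**1. Does the run fall inside each measured quantity?**

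- *Procedure time.* The run is made while the guidewire is still in place (Protocol 6.5.3.2), and the clock stops at guide catheter removal (endpoint 12 in both documents). It is inside by definition, whichever starting point is used.
- *Fluoroscopy time and radiation.* These stand in the same item, with no exclusion.
- *Contrast use.* Endpoint 13 is unqualified and the SAP summary is by arm. The run is inside as written.
- *Procedural cost.* Section 6.9 converts procedural duration into cost, so the added time carries through.
- *Device usage (endpoint 11).* The list covers stents, balloons and inflation pressure. An imaging catheter is not on it, so this endpoint is unaffected.
- *Imaging catheter in the cost model.* Not stated. Section 6.9 gives an open list of example devices that does not name it. If the catheter is costed in both arms, one cancels. If it is costed in neither, the OCT arm's catheter is missing. Only costing it in the OCT arm alone matches the stated aim, and no visible text says that.

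**2. How much contrast?**

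Inputs, all from Protocol 6.5.3.3:

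- Volume per run, v. For the left coronary artery, "the recommended contrast injection volume is 14 ml at an injection rate of 4 ml/s in the left coronary artery". The right coronary figure is 12 mL. For large or tortuous vessels or distal lesions it is 4 mL/s × 4 s = 16 mL. The range is therefore 12–16 mL.
- Runs per target vessel in the OCT arm, k: at least 2 (before and after stenting), with another after each further optimisation. Values of k above 2 are assumptions here.
- Runs per target vessel in the angiography arm: 1.

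The volumes are given for the OCT arm. Section 6.5.3.2 gives none for the blinded run, so the same v is assumed. Runs are assumed to be additive to all other contrast.

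Difference as recorded = (k − 1)v. Difference without the research run = kv. Share lost = v / kv = 1/k.

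| k | As recorded, (k − 1)v | Without research run, kv | Share of OCT-run contrast lost |
|---|---|---|---|
| 2 | 12–16 mL | 24–32 mL | 1/2 = 50% |
| 3 | 24–32 mL | 36–48 mL | 1/3 = 33% |
| 4 | 36–48 mL | 48–64 mL | 1/4 = 25% |

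The absolute shortfall is v, or 12–16 mL per target vessel. With two target vessels it is 2 × 12 to 2 × 16 = 24–32 mL.

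No such calculation is possible for time or cost: the documents give neither the minutes for a run nor a catheter price.

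**The case against.** The strongest reply is that much of the economic plan cannot be seen. Resource data come from case report forms, and that appendix is redacted. Parts of the SAP are blacked out, and the protocol defers to standardized costing methods. A separate field or an exclusion could sit in any of these. This stands for cost, and it limits the claim to what the visible plan does. It is weaker for procedure time, because both definitions are readable and neither has an exclusion.

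Several stronger readings are tempting, and the documents do not support them:

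- *That the catheter count is equal in both arms, so its cost difference is near zero.* This assumes that the research catheter is charged to the angiography arm, which no passage says.
- *That half of the added contrast is lost.* The shares apply to contrast from OCT runs only. Total contrast also depends on extra dilatation and stenting prompted by OCT, which the formula ignores. Additivity is doubtful too. Section 6.5.3.3 requires cine angiography during the pullback to make use of the contrast, and the blinded run comes when completion angiography would be taken anyway. It may replace part of an injection.
- *That the values just before the blinded run could serve as the angiography arm's end-of-procedure values.* This would also cut completion angiography and guide removal from that arm alone, and would bias the comparison the other way.
- *That the nephropathy comparison is conservative for harm.* Extra control-arm contrast moves the arms closer together, so OCT-related harm may be understated.

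It is also fair to say that these endpoints are non-powered and that the run is openly described.

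**Conclusion.** The point holds for procedure time, by both definitions. It holds for contrast, fluoroscopy and radiation as those endpoints are written, and for procedural cost through the duration term. For cost the finding is that the visible plan does not separate or remove the run; whether redacted material does so cannot be judged. The direction favours OCT guidance throughout.

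The only part that can be sized is OCT-run contrast. The shortfall is 12–16 mL per target vessel, which is 50% of the OCT-run difference at the protocol minimum of two runs and smaller with more. It rests on equal volumes per run and additivity. The nephropathy comparison is diluted for the same reason, by an amount the documents do not allow one to estimate.

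MSA, TVF and the major secondary endpoint are unaffected. This is an inexpensive improvement to secondary and economic results, and does not threaten the trial's main conclusions.

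**What to change.** In Protocol 6.9, endpoints 12–13 and SAP 5.5 items 12–13:

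- Record the blinded run's own start and end time, contrast volume, fluoroscopy time and radiation.
- Subtract only those amounts from the angiography arm. Keep completion angiography and guide removal in both arms.
- Cost the OCT catheter in the OCT arm, and exclude the research catheter from the angiography arm.
- Report the all-in values alongside the adjusted ones.
- State that the contrast-nephropathy comparison is against angiography plus at least one OCT run, that subtraction cannot correct it, and that it may understate OCT-related harm.

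The starting point of procedure time should be reconciled between the two documents in the same edit.

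The cost is a few case report form fields and short additions to the text. The fields must be filled at the procedure, since the values may not be recoverable later. The sponsor should expect a less favourable reported increment in time, contrast and cost for OCT guidance. Clinical management does not change.
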